Title of the study: Third generation cryotherapy reduces time to surgery and local complication in patients with ankle fractures: a prospective randomized controlled trial.

Type of the Paper: Randomized Controlled Trial.

NCT number: not available

Article ID: cryotherapy012021.n01

Date of the document: 24/04/2024

This is a RCT about the preoperative use of third generation cryotherapy in patients hospitalized for ankle fracture. The aim of this study is to assess the effects of third generation cryotherapy on time to surgery, pain, opioids intake, and local skin complications. Although the use of cryotherapy is traditionally believed to reduce pain, swelling, local skin complications and the need of analgesia, the results on ankle surgery are not well reported and still contradictory. The working hypothesis is that third generation cryotherapy is a safe, reduces time to surgery and is useful in the surgical management of ankle fractures

We confirm that each author of this article meets the journal's criteria for authorship. We confirm that the manuscript has not been submitted or is not simultaneously being submitted elsewhere, and that no portion of the data has been or will be published in proceedings or transactions of meetings or symposium volumes.

Fiximed Italia, Rome, Italy, funded the APC, but the company had no role in the design of the study, in the collection, analyses, or interpretation of data, in the writing of the manuscript, and or in the decision to publish the results.

The authors declare no external funding or other benefits from commercial sources for the work reported on in the manuscript, nor any other financial interests which could create a potential conflict of interest.

Thank you

Kind regards

Third generation cryotherapy reduces time to surgery and local complication in patients with ankle fractures: a prospective randomized controlled trial.

Study protocol and statistical analysis

We analyzed the prospectively collected data of 169 patients with ankle fracture, treated with open reduction and internal fixation (ORIF). Patients were randomized in two groups at the time of the diagnosis in the emergency department. The treatment group (T: 89 patients) were treated with a third-generation cryotherapy device (Z- One®, Zamar) which was applied daily for 2 hours two times a day up to the day of surgery. The leg was immobilized in a walking boot which was removed when the cryotherapy device was applied. The control group (C: 80 patients) did not use cryotherapy before surgery, the leg was immobilized into a half cast and elevation of the injured limb was indicated. Patients were collected in two different hospitals (Azienda Ospedaliera San Camillo Forlanini -Roma and Ospedale San Paolo – Civitavecchia) between 2021 and 2023. All patients had signed a written consent, and the study was approved by the local ethic committee.

Inclusion and exclusion criteria

Patients admitted to the emergency department with an ankle fracture were included in the current study. Exclusion criteria were open fractures, fracture-dislocations which required external fixation, patients with one or more associated fractures, and patients with a diagnose of major trauma. Patients who were not able to complain with the pre and post-surgical indications were also excluded.

Patients' assessment

A detailed physical examination was conducted in all patients, who were examined in the emergency department by local orthopedic surgeons. All patients underwent standard radiographs to diagnose the fracture, and computed tomography for the preoperative planning if indicated. After the diagnosis was made and surgical treatment was indicated, the patient was hospitalized in the department of orthopedic and trauma surgery. Patients of group T were immobilized in a walking boot to allow the use of the cryotherapy device. Patients belong to group C were immobilized in a half cast. Pain was evaluated according to the Visual Analogue Scale (VAS) and the analgesic drug demand (including morphine or acetaminophen). The Body Mass Index (BMI), number of cigarettes smoked, presence of preoperative skin complications were assessed on a daily basis.

Surgical technique

Under loco-regional anesthesia, the patient was positioned supine with a little rise under the buttock, or in prone decubitus if posterolateral surgical approach was indicated to reduce the posterior malleolus. A tourniquet was applied at the tight, and the lower limb was prepared and draped in the usual sterile fashion. Lateral malleolus was approached first, reduced and fixed with a plate and screws. Then, surgical technique varied depending on the pattern of fracture, distal tibiofibular syndesmosis injury or associated soft tissue injury, as deltoid ligament rupture.

All patients received intraoperative antibiotic treatment, intravenous controlled analgesia for 24–48h after surgery, and standard thromboembolic prophylaxis with low molecular weight heparin (LMWE) for up to complete weight bearing. Passive motion of the ankle was encouraged from the first post-operative day.

Statistical analysis

A power analysis was performed to evaluate the sample size necessary to guarantee a power of at least 0.9 with a significance level of 0.05 using preliminary data on time to surgery.

Univariate descriptive analysis of the variables under study was carried out by calculating the centrality and variability indices for the quantitative variables and frequency tables for the variables. The homogeneity of the control group and the treatment group for the variables sex, age, type of fracture, diabetes, hypercholesterolemia, venous insufficiency, and BMI class were checked. Depending on the nature of the variables, a t-test or a chi-square test was used.

Any significant differences between the treatment and control groups were assessed using independent samples t-tests for quantitative variables and chi-square tests for qualitative variables. Where the sample size is not sufficient, the non-parametric Mann-Whitney test for independent samples was used.

An alpha significance level of 0.05 was used in all analyses mentioned. For the statistical analysis of data, IBM SPSS Statistics software version 28 was used.

CONSORT 2010 Flow Diagram

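### The working hypothesis calls the device safe, but no interval or bound on harm is planned, so a non-significant test on preoperative skin complications could not support that word

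*Combined protocol and SAP*

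**What the plan says.** The cover text states the working hypothesis that "third generation cryotherapy is a safe, reduces time to surgery and is useful in the surgical management of ankle fractures". It does not define safe. The aim, in the same text, treats skin complications as an outcome that the device may affect: "The aim of this study is to assess the effects of third generation cryotherapy on time to surgery, pain, opioids intake, and local skin complications". The title goes further and claims a reduction: "Third generation cryotherapy reduces time to surgery and local complication in patients with ankle fractures".

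Under Patients' assessment, the only complication variable is described by the words "presence of preoperative skin complications were assessed on a daily basis". The document describes no adverse-event collection, no postoperative complication outcome and no record of what caused a skin event.

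Under Statistical analysis, variables are first summarised descriptively, with frequency tables. Then "Any significant differences between the treatment and control groups were assessed", using "independent samples t-tests for quantitative variables and chi-square tests for qualitative variables", with the Mann-Whitney test as the fallback where the sample is too small. On the error rate: "An alpha significance level of 0.05 was used in all analyses mentioned". The sample size was chosen for "a power of at least 0.9 with a significance level of 0.05 using preliminary data on time to surgery". The section mentions no confidence interval, acceptable excess risk or margin, and does not say how a null result on skin complications would be interpreted.

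**The concern.** A hypothesis of safety needs an analysis that can limit how much harm remains plausible. The plan offers a count in each arm and a test of no difference. If that test is not significant, the data may fit no effect, some benefit or a material excess of skin complications, and nothing in the plan separates these cases. The sample size gives no reassurance, because it was fixed for another outcome.

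The scope of the claim matters too. Safe, without qualification, covers more than preoperative skin findings, and so does the title's local complication, which omits both *skin* and *preoperative*. At stake is a conclusion about harm that goes beyond what was measured and planned.

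**Working it through.** **Inputs from the document.** Group T has 89 patients and group C has 80. The test is chi-square at alpha 0.05. Sidedness is not stated, so two-sided is assumed.

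**Inputs assumed.** No skin complication rate is given. Control rates from 2% to 20% are used to show the range.

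**The plan's own figure.** The power of at least 0.9 for time to surgery cannot be reproduced, because no effect size, standard deviation or target number is given. Solving backwards, 1/80 + 1/89 = 0.02374, and √0.02374 × (1.960 + 1.282) ≈ 0.50. So 89 versus 80 gives 90% power for a standardised difference of about 0.50. This says nothing about skin complications.

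**Power of the difference test.** For every pair of event counts (a of 80, b of 89), with p̄ = (a + b)/169, compute

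χ² = (a/80 − b/89)² / [p̄(1 − p̄)(1/80 + 1/89)]

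Then sum the binomial probabilities of the pairs with χ² > 3.84. The true group T rate is set at twice the control rate.

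| Assumed control rate | Group T rate | Power to detect the doubling |
|---|---|---|
| 2% | 4% | 8% |
| 5% | 10% | 23% |
| 10% | 20% | 44% |
| 15% | 30% | 65% |
| 20% | 40% | 81% |

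Power passes 50% at a control rate of about 11.5%. At 5% versus 10%, Fisher's exact test, which the plan does not name, would have 18% power.

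**Precision if the rates are equal.** Half-width = 1.96 × √[p(1 − p) × 0.02374].

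- p = 5%: 1.96 × √(0.0475 × 0.02374) = 6.6 points
- p = 10%: 1.96 × √(0.09 × 0.02374) = 9.1 points
- p = 15%: 1.96 × √(0.1275 × 0.02374) = 10.8 points
- p = 20%: 1.96 × √(0.16 × 0.02374) = 12.1 points

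**A hypothetical result.** Suppose 4/80 (5.0%) in group C and 9/89 (10.1%) in group T. Then p̄ = 13/169 = 0.0769 and χ² = 0.0511² / (0.0769 × 0.9231 × 0.02374) ≈ 1.55, well below 3.84. The difference is 5.1 points. Its standard error is √(0.05 × 0.95/80 + 0.101 × 0.899/89) = 0.0402, so the 95% interval is 5.1 ± 7.9, or −2.8 to 13.0 points. The planned output would be two frequencies and a non-significant test. The interval shows that an excess of up to 13 points has not been excluded.

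**Events seen only in group T.** For an event type with none among 89, the exact upper limit is 1 − 0.05^(1/89) = 3.3% (one-sided 95%) or 1 − 0.025^(1/89) = 4.1% (two-sided 95%). With one event, the limits are 5.2% and 6.1%. These apply only if such events can be identified in the records.

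**The case against.** The strongest reply is that a difference test suits the stated aim. Skin complications are listed as an effect to be assessed, and the title claims a reduction. A significant reduction would be direct evidence about preoperative skin complications. This stands, and it confines the point to a null result. The evidence would, however, concern the whole preoperative package, because the arms also differ in immobilisation (walking boot versus half cast).

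Second, frequency tables are planned, so per-arm counts will be available. This also stands. What is missing is the interval, not every form of estimate.

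Four stronger readings are tempting, but the documents do not support them:

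- *That the investigators will read non-significance as safety.* No section sets that rule, and the sentence quoted is a working hypothesis, not a conclusion.
- *That most trials of this size would miss a doubling.* This holds only at control rates below about 11.5%. At 20%, about four in five would detect it.
- *That the trial cannot show safety at all.* With equal true rates of 5 to 20%, 169 patients would exclude a 15-point excess with 68 to 99% power, but a 5-point excess with only 13 to 32%. Whether either is enough depends on a tolerance that the plan never states.
- *That device-caused events can simply be separated out.* Only the presence of skin complications is described, not their cause. Attribution made afterwards, with no blinding described and different immobilisation in the two arms, could be unreliable.

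**Conclusion.** The point holds in limited form. The plan hypothesises safety without defining a safety outcome or planning an interval or bound on harm, and it records one complication variable. A non-significant chi-square result on that variable could not support the word safe, and a significant reduction would support only a statement about preoperative skin complications.

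The size depends on an event rate that the documents do not give. Over assumed control rates of 2 to 20%, the chance of detecting a doubling runs from 8% to 81%. Over equal true rates of 5 to 20%, the interval would extend about 7 to 12 points either side of the estimate. These figures assume a two-sided 0.05 level, the uncorrected chi-square test, and all 89 and 80 patients analysed.

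The point concerns what may be concluded. It does not suggest that the device is harmful, and it does not affect the analysis of time to surgery.

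**What to change.** 1. Report the between-arm risk difference for preoperative skin complications with its 95% confidence interval, beside the chi-square test.
2. State in the analysis section that a non-significant test is not evidence of safety.
3. Drop safe from the hypothesis and conclusions, or limit it to preoperative skin complications and to what the interval excludes.
4. Reword the local complication claim in the title and conclusions as preoperative skin complications.
5. Report device-attributable skin events separately, with an exact upper limit, only if the cause was recorded at the time of assessment. If it was not, report the overall risk difference alone.

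No non-inferiority margin is proposed. Patients were collected between 2021 and 2023 and the document is dated April 2024, so a margin chosen now would be post hoc.

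The cost is wording and one interval from counts already planned, with no new patients. Item 5 adds a check of the records. The downside is a less favourable headline.

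### Walking boot versus half cast coincides with treatment arm, so the trial cannot attribute an effect to cryotherapy itself as its title, aim and hypothesis do

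*Combined protocol and SAP*

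**What the plan says.** The opening paragraph of *Study protocol and statistical analysis* describes the treatment group (T, 89 patients) as receiving cryotherapy for two hours twice a day until surgery, and adds: "The leg was immobilized in a walking boot which was removed when the cryotherapy device was applied". Of the 80 controls (group C) the same paragraph reports that they "did not use cryotherapy before surgery, the leg was immobilized into a half cast and elevation of the injured limb was indicated".

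*Patients' assessment* repeats the difference and gives a reason for the boot: "Patients of group T were immobilized in a walking boot to allow the use of the cryotherapy device". For controls it says: "Patients belong to group C were immobilized in a half cast". It does not say why controls could not also wear a boot.

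The covering text at the front of the document attributes the effect to cryotherapy:

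- Title: "Third generation cryotherapy reduces time to surgery and local complication in patients with ankle fractures".
- Aim: to "assess the effects of third generation cryotherapy on time to surgery, pain, opioids intake, and local skin complications".
- Hypothesis: "The working hypothesis is that third generation cryotherapy is a safe, reduces time to surgery".

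The *Statistical analysis* section compares the arms as wholes: "Any significant differences between the treatment and control groups were assessed using independent samples t-tests", with chi-square and Mann-Whitney tests as the alternatives. Nowhere does the document call the intervention a package or list immobilisation type as a limitation.

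**The concern.** Two things differ between the arms by design: whether the ankle is cooled, and what holds it until surgery. A boot taken off twice a day and a half cast could plausibly differ in their effect on skin, pain and analgesic use, all of which the trial assesses. Time to surgery, the outcome used for the power analysis, would also be affected if immobilisation changes the soft tissues and soft-tissue condition influences when surgery is done. Both links are assumptions; the document gives no criterion for timing surgery.

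The distortion could go either way. A boot advantage would be credited to cryotherapy, and a boot disadvantage would hide part of a real cryotherapy effect. A hospital that already uses removable boots, or could switch to them without buying the device, needs to know which component did the work. This trial cannot tell it.

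**Working it through.** **1. What differs between the arms**

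| | Group T (n = 89) | Group C (n = 80) |
|---|---|---|
| Cryotherapy | 2 h, twice daily | none |
| Immobilisation | walking boot, off during sessions | half cast |
| Elevation | not mentioned | indicated |

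The document describes neither a boot-only arm nor an arm with cryotherapy and a half cast. Silence on elevation in group T is a reporting gap; it does not show that those limbs were not elevated.

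**2. What can be estimated**

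Write the outcome as

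Y = μ + γ·(cryotherapy) + β·(boot) + error.

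Both indicators equal 1 for all of group T and 0 for all of group C. The expected difference between arms is therefore γ + β. The design matrix (169 rows; columns for intercept, cryotherapy and boot) has rank 2 for its 3 columns. Only the sum γ + β is estimable, and covariate adjustment cannot change that.

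**3. Inputs for an illustration of size**

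- n = 89 and 80 (opening paragraph); 89 + 80 = 169, which matches the stated total.
- Significance level 0.05 and power of at least 0.9 (*Statistical analysis*). Sidedness is not stated; two-sided is assumed.
- The planned effect and SD are not given, so the plan's sample size cannot be reproduced. Effects are expressed in SD units.
- Boot-versus-cast effect b: not in the documents. Assumed values are 0 to 0.3 SD in either direction, positive favouring T.

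**4. Precision of the comparison (t-test, df = 167)**

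- Standard error = √(1/89 + 1/80) = 0.154 SD.
- Smallest significant difference = 1.974 × 0.154 = 0.304 SD.
- Difference detectable with 90% power = 0.502 SD.

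**5. Probability of a significant result favouring T**

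This is the probability that a noncentral t with 167 df and noncentrality (γ + b)/0.154 exceeds 1.974.

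| Cryotherapy effect γ | b | γ + b | Probability |
|---|---|---|---|
| 0 | 0 | 0 | 2.5% |
| 0 | +0.1 | 0.1 | 9.4% |
| 0 | +0.2 | 0.2 | 25.2% |
| 0 | +0.3 | 0.3 | 49.0% |
| 0.502 | 0 | 0.502 | 90.0% |
| 0.502 | −0.1 | 0.402 | 73.8% |
| 0.502 | −0.2 | 0.302 | 49.6% |
| 0.502 | −0.3 | 0.202 | 25.6% |

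With γ = 0 and b negative, the same 9.4%, 25.2% and 49.0% apply to a significant result favouring C.

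**6. Effect on the estimate**

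Hold cryotherapy at 0.502 SD. The expected observed difference is 0.502 − 0.3 = 0.202 SD at b = −0.3, and 0.502 + 0.3 = 0.802 SD at b = +0.3. The cryotherapy effect is then 0.502/0.202 = 2.5 times, or 0.502/0.802 = 0.63 times, the expected difference.

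**The case against.** The strongest reply is that the boot is part of delivering the treatment. The device goes on the leg twice a day, so the immobilisation must come off, and anyone adopting the regimen as described adopts the boot too. On that reading the trial is a valid pragmatic comparison of two management strategies. Both immobilisation types are openly stated, and a trial is often named after its active component. There is then no bias in the randomised contrast; bias arises only if the target is cooling alone.

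Much of this stands. The package comparison is valid, and the tests are not at fault for failing to separate what the design joined. However, the stated reason explains only why group T needed something removable. Nothing in the document rules out a boot for controls, which would have isolated cryotherapy. If the package is the intended question, the title, aim and hypothesis should say so.

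It is also fair that the probabilities above are simply the power curve of a t-test with these arm sizes, and would look the same for any co-intervention of the assumed strength. They are not evidence that a boot effect exists. The identifiability problem does not depend on them.

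Finally, a caveat may appear in the separate manuscript that the covering text refers to. That would not correct the wording of this document.

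**Conclusion.** The concern holds. The trial estimates the effect of cryotherapy plus a removable boot against a half cast without cryotherapy. The claim about cryotherapy itself is not identified, and no reanalysis of these data can identify it. This follows from the arm descriptions alone and needs no assumption about effect size.

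How far the package effect departs from the cryotherapy effect is unknown in both size and direction. Under the assumed range of 0.3 SD either way and a two-sided t-test, the boot alone could produce a significant result favouring T up to 49% of the time, or reduce the chance of detecting a 0.50 SD cryotherapy effect to 26%. The randomised comparison of the packages is unaffected, so this should be fixed but does not invalidate the trial.

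**What to change.** Patients were collected between 2021 and 2023 and the document is dated 24/04/2024, so the arms cannot be changed. The wording can:

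- State the title, aim, working hypothesis and any later conclusion as the effect of *cryotherapy plus removable walking boot versus half cast without cryotherapy*, and do not attribute the effect to the device alone.
- Add one sentence naming immobilisation type as an inseparable part of the contrast.
- State whether group T limbs were also elevated. Name elevation as part of the contrast only if they were not.

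The cost is a few edits to the text. No new data, sample size or tests are needed. The price is a narrower claim.

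### Were randomised patients dropped from the analysis because they did not reach ORIF or did not comply?

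*Combined protocol and SAP*

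**What the plan says.** The opening paragraph of the combined protocol and SAP (Study protocol and statistical analysis) fixes the time of allocation: "Patients were randomized in two groups at the time of the diagnosis in the emergency department". The same paragraph describes the analysed cohort by the operation it received: "We analyzed the prospectively collected data of 169 patients with ankle fracture, treated with open reduction and internal fixation (ORIF". It gives 89 patients in the cryotherapy group (T) and 80 in the control group (C). The device belongs to group T only, "which was applied daily for 2 hours two times a day up to the day of surgery".

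Under Inclusion and exclusion criteria the entry condition is broad: "Patients admitted to the emergency department with an ankle fracture were included in the current study". Then come four exclusions: open fractures, fracture-dislocations needing external fixation, associated fractures, and major trauma. The list ends with "Patients who were not able to complain with the pre and post-surgical indications were also excluded".

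Patients' assessment gives the path to the ward: "After the diagnosis was made and surgical treatment was indicated, the patient was hospitalized in the department of orthopedic and trauma surgery".

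The Statistical analysis section goes directly to the tests ("Any significant differences between the treatment and control groups were assessed using independent samples t-tests for quantitative variables", with chi-square and Mann-Whitney alternatives). It names no intention-to-treat, all-randomised or per-protocol set. The document ends with the heading of a CONSORT flow diagram, whose content is not in the text available here.

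**The concern.** Read together, these statements leave room for selection after allocation. ORIF is not an entry criterion, and whether a patient received it is known for certain only after randomisation. The compliance clause also covers post-surgical instructions. Actual compliance with those, for example early mobilisation ("Passive motion of the ankle was encouraged from the first post-operative day"), can be observed only after time to surgery has been recorded.

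If either condition was applied after allocation, losses could differ by arm, because only group T had two 2-hour device sessions a day to comply with. A patient who waits longer has more sessions to miss, so dropping non-compliers from T could remove its slower patients and shorten its mean time to surgery with no treatment effect. Time to surgery and local complications are the outcomes in the title, and time to surgery is the variable behind the power analysis. With no analysis population named, nothing in the statistical section expressly rules this out.

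**Working it through.** **1. What the text supports on timing**

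| Statement | Section | Screening reading | Post-randomisation reading |
|---|---|---|---|
| Unable to comply, excluded | Inclusion and exclusion criteria | Follows four baseline fracture or trauma features and continues the same list; inability is a capacity that can be judged at presentation | Possible only if inability is taken to mean observed non-compliance |
| Cohort treated with ORIF | Opening paragraph | Describes surgical candidates: the cover text speaks of hospitalised patients and preoperative use, and hospitalisation follows the surgical indication | Possible if allocation preceded the decision to operate; the order is not stated |
| 89 in T, 80 in C | Opening paragraph | 89 + 80 = 169, the analysed total, given straight after the sentence saying patients were randomised into two groups | Would need a larger, unreported number randomised |

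No sentence describes a randomised patient who was removed, or one who did not reach surgery.

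**2. Does the split suggest unequal loss?** For 89 of 169 under 1:1 simple randomisation (an assumption; the allocation method is not given), the two-sided binomial p is 0.54. The split gives no sign of it, though this test could not detect small losses.

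**3. How large could the bias be if there were losses?** The documents report none, so the loss rates, the normal outcome and the two-sided 0.05 test are assumptions. Analysed numbers stay at 89 and 80, there is no true effect, and losses come from T only: 5 of 94 (5%) or 10 of 99 (10%).

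- Standard error of the difference, in SD units: √(1/89 + 1/80) = 0.154.
- If the m lost patients average δ SD slower than all randomised T patients, the remaining T mean falls by m·δ/89.
- Type I error = Φ(−1.96 + shift/0.154) + Φ(−1.96 − shift/0.154).

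| Lost from T | δ | Shift (SD) | Shift/SE | Type I error |
|---|---|---|---|---|
| 5 of 94 | 0.5 | 0.028 | 0.18 | 5.4% |
| 5 of 94 | 1.0 | 0.056 | 0.36 | 6.5% |
| 10 of 99 | 0.5 | 0.056 | 0.36 | 6.5% |
| 10 of 99 | 1.0 | 0.112 | 0.73 | 11.3% |

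For extreme selection, simulation (40,000 to 60,000 trials per scenario, pooled t-test) gives:

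| Losses | Shift (SD) | Type I error |
|---|---|---|
| None | 0 | 5% |
| T loses its slowest 5 of 94 | 0.11 | 13% |
| T loses its slowest 10 of 99 | 0.19 | 28% |
| T loses 10 of 99, five slowest and five at random | 0.11 | 12% |
| T loses its slowest 10 of 99, C its slowest 4 of 84 | 0.09 | 13% |
| About 5% slowest lost in both arms | 0.01 | 7% |

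For scale, the difference that 89 vs 80 detects with 90% power is (1.960 + 1.282) × 0.154 = 0.50 SD. This is a back-calculation; the plan gives no effect size.

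**The case for a change.** The strongest case for a change is that a randomised trial should name its analysis population, and this one does not. Time to surgery is undefined for a patient who never has surgery, so a rule for such patients is needed even if the compliance clause is pure screening. A flow diagram would count exclusions but would not say which set is primary. A few sentences would settle all of this.

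Much of that stands as a comment on reporting. The timing of the compliance judgement, the order of surgical indication and allocation, and the analysis set are all unstated. It does not show that the plan gives a wrong result. A rule for patients who do not reach surgery matters only if there were any, and the text mentions none. The flow diagram is the place for numbers randomised, excluded and analysed; its content is lost from this copy, so those counts cannot be called missing. Recruitment between 2021 and 2023 is reported as past in a document dated 24/04/2024, so a censoring or competing-event rule could no longer be set in advance. It would also replace the planned t-test to serve patients not known to exist.

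**Conclusion.** No change to the plan follows. The wording leaves a gap in detail, but the natural reading fills it: compliance was a baseline screening criterion, and the 169 are the patients randomised, 89 and 80, compared in the arms to which they were allocated. On that reading there is no selection after randomisation, type I error stays at 5%, and a clarifying sentence would alter no result.

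The conclusion rests on that reading and on the absence of any described removal. If the flow diagram showed more than 169 randomised, the question would reopen. Its size would then depend on numbers and reasons: about 5% to 11% type I error if 5% or 10% were lost from T alone and averaged 0.5 to 1 SD slower, and 13% to 28% only if all of them were the slowest in that arm. Nothing in the readable text points to either.

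### The timing of the VAS reading and any pre-treatment baseline are unspecified, and pain is compared without adjustment, so the pain result is valid but less precise than it could be

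*Combined protocol and SAP*

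**What the plan says.** The opening statement of the combined document lists pain among four effects to be assessed, with time to surgery, opioid intake and local skin complications. Randomisation took place in the emergency department when the fracture was diagnosed.

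Under Patients' assessment, the text covers the emergency department examination, imaging, admission and the arm-specific immobilisation ("Patients of group T were immobilized in a walking boot to allow the use of the cryotherapy device", with a half cast for controls). It then describes pain: "Pain was evaluated according to the Visual Analogue Scale (VAS) and the analgesic drug demand (including morphine or acetaminophen"). That sentence names the instruments but no time point. The daily schedule belongs to the next sentence, which covers BMI, cigarettes and skin complications.

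Under Statistical analysis, the homogeneity check covers sex, age, fracture type, three comorbidities and BMI class. Entry pain is not in it. Group differences are "assessed using independent samples t-tests for quantitative variables and chi-square tests for qualitative variables", with a Mann-Whitney test where numbers are too small. VAS is not named there; it comes under the general rule for quantitative variables. No covariate-adjusted, change-score or repeated-measures analysis is described.

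**The concern.** How much a patient hurts in the days after an ankle fracture plausibly depends in part on how painful the injury was at entry. If so, a raw two-sample comparison leaves that variation in the error term, and the interval for the pain effect is wider than it needs to be. Because entry pain is not tabulated either, a reader cannot see whether the arms happened to differ on it.

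There is also a more basic gap. With no time point or summary named (a given day, the peak, a mean over the stay), the quantity entering the t-test is undefined.

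The sample size gives no reassurance on pain, because the power calculation was made "using preliminary data on time to surgery". Precision that could be had cheaply is therefore worth having.

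**Working it through.** **The plan's own figure.** The plan states "power of at least 0.9 with a significance level of 0.05 using preliminary data on time to surgery". It gives no effect size or SD, and nothing for pain, so this figure can be neither confirmed nor refuted. What the achieved numbers can detect can be worked out instead.

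**Inputs from the document.**
- Total: "We analyzed the prospectively collected data of 169 patients with ankle fracture".
- Arms: "The treatment group (T: 89 patients") and 80 controls; 89 + 80 = 169.
- Alpha: "An alpha significance level of 0.05 was used in all analyses mentioned". Two-sided testing is assumed, since the plan does not say.

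**Input assumed.** The within-arm correlation r between entry and later VAS is not given. The range 0.2 to 0.7 is used.

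**Step 1: precision of the raw comparison, in SD units.**
- SE = √(1/89 + 1/80) = 0.154.
- 95% half-width = 1.96 × 0.154 = 0.302.
- Difference detectable with 80% power = (1.960 + 0.842) × 0.154 = 0.432.
- Difference detectable with 90% power = (1.960 + 1.282) × 0.154 = 0.499.

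**Step 2: effect of adjusting for entry VAS.** ANCOVA multiplies the residual variance by (1 − r²) and the interval width by √(1 − r²). The equivalent sample size is 169/(1 − r²). Power at a true difference of 0.432 SD is Φ(0.432/[0.154 × √(1 − r²)] − 1.96).

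| r (assumed) | Variance factor | Interval width factor | Narrowing | Equivalent N | Extra patients | Power (raw t-test 80%) |
|---|---|---|---|---|---|---|
| 0.2 | 0.96 | 0.980 | 2% | 176 | 7 | 81.6% |
| 0.3 | 0.91 | 0.954 | 5% | 186 | 17 | 83.6% |
| 0.5 | 0.75 | 0.866 | 13% | 225 | 56 | 89.9% |
| 0.7 | 0.51 | 0.714 | 29% | 331 | 162 | 97.5% |

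**Step 3: chance imbalance.** A difference in mean entry VAS between arms has expectation zero and an SE of 0.154 SD. An imbalance of 1.96 SE (0.302 SD) would shift the unadjusted pain difference by r × 0.302, which is 0.09, 0.15 or 0.21 SD at r = 0.3, 0.5 or 0.7. An imbalance that large or larger, in either direction, arises in about 5% of randomisations, so these are tail values. They are also already counted in the t-test's SE: the raw variance, 0.154², splits into r² × 0.154² from entry pain and (1 − r²) × 0.154² from everything else. Adjustment removes the first part.

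**The case against.** A reader might infer that pain was read only after arm-specific care had begun, and that no entry reading exists. The documents do not support either. The inference rests on sentence order alone, and the order is a poor guide to chronology: BMI and smoking come later still in the same paragraph, yet nobody would conclude that they were first known after the boot or cast. The paragraph opens with an examination in the emergency department, and a pain score there is neither described nor excluded. All that can be said is that the timing is unspecified.

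A reader might also infer that the pain comparison is biased. It is not biased on this account. Randomisation makes the unadjusted test valid, and its error rate allows for chance imbalance in entry pain (step 3).

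Three further objections carry weight. First, the size depends wholly on r. Nothing in the documents supports 0.5 or 0.7, and analgesia given on demand could weaken the link between entry and later scores. At 0.2 or 0.3 the gain is slight. Second, pain is not the outcome used for the power analysis; it is absent from the title, and the working hypothesis does not name it. Third, enrolment ran from 2021 to 2023 and the document is dated 24/04/2024, so a new question at enrolment is no longer possible, and any change to the analysis is now post hoc.

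These points limit the size of the concern and the available remedy. They do not supply the missing definition of the pain outcome or the missing baseline.

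**Conclusion.** The point holds as one of specification and precision. For a named aim, the plan does not say when VAS was read or which reading is analysed, defines no pre-treatment value, does not check balance on it and does not use it.

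The unadjusted comparison is valid. The precision forgone is about 2% to 5% of interval width if r is 0.2 to 0.3, 13% at 0.5 and 29% at 0.7. These figures assume a linear relation with a common slope in both arms and an entry score for every patient. The direction follows from any non-zero correlation; the size cannot be settled from the documents. Nothing here bears on time to surgery or skin complications.

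**What to change.** - State when VAS was read, and name the single reading or summary that is the pain outcome.
- Search the charts for a VAS or triage pain score recorded in the emergency department before the boot, cast or first cold session, noting any analgesic already given. A score from before allocation is preferable.
- Tabulate that score by arm, with the number missing.
- Analyse the named VAS outcome by ANCOVA with the entry score as covariate. Use a missing indicator or a mean-imputed baseline for patients without a score, so that nobody is dropped. Report the adjusted difference and interval beside the planned t-test, and label the analysis post hoc.
- Do not use a reading taken after the first session as the baseline. It may already reflect treatment, and adjusting for it could remove part of the effect.
- If no entry scores were recorded, state that as a limitation of the pain result.

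The cost is a chart search and one covariate. Some entry scores will probably be missing, and the gain in the table shrinks as the share of patients with a score falls.
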